5.3 Hypothesis

Hi. The implementation of an aerobic physical exercise program for eight weeks will have effects on at least one of the levels of metabolic disorders such as: the reduction of blood pressure, abdominal obesity, altered glucose levels, and increasing HDL in the study population

H0. The implementation of an aerobic physical exercise program for eight weeks will not have effects on any of the levels of metabolic disorders such as: the reduction of blood pressure, abdominal obesity, altered glucose levels, and increasing HDL in the study population

6. Methods and materials

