6.3. Selection criteria

Table 4. Selection criteria

Inclusion	Exclusion	Elimination
University of Colima students linked to the central campus.	Motor limitations that may hinder the performance of physical exercise.	Musculoskeletal injuries during the study period.
Students aged between 18		Unforeseen Medical Events: Unexpected medical

and 25 years old.	Pregnancy or lactation.	situations that could influence study results, such as hospitalizations, serious illnesses, or surgeries.
Authorization to participate in the project with a signed informed consent.	High Vigorous Physical Activity Level according to the IPA-Q.	Non-Compliance with Follow-Up: Subjects failing to meet a minimum of 80% (19 out of 24 sessions) of the stipulated physical conditioning program time.
Suffer from at least one of the parameters of metabolic disorders or cardiovascular risk (Hyperglycemia, decreased DHL, elevated triglycerides, abdominal obesity or hypertension) following the clinical assessment (Considering the criteria established by the ADA and ATPIII).	To be currently under pharmacological treatment to manage altered metabolic levels.	Initiation of clinical treatment that may affect protocol results, such as medications that reduce alterations.
		Participants who voluntarily withdraw from the study.

Source: self-made.

7. Variable operationalisation.

Table 5. Dependent variables.

Dependent variables	Operational definition	Nature	Scale	Instrument
Glucose Alterations	Fasting plasmatic glucose concentration determination:	Quantitative Continuous Ratio	It is considered an alteration >110 mg/dl	Fasting serum glucose

Abdominal Circumference	Total abdominal perimeter Abdominal obesity based on abdominal circumference.	Quantitative Continuous Ratio	It is considered an alteration when: Males >90cm Females >85 cm	Circumferential measurement with ISAK tape measure
HDL (High-Density Lipoprotein)	Serum concentration of high-density lipoprotein in milligrams per deciliter (mg/dl)	Quantitative Continuous Ratio	It is considered an alteration when: Males < 40 mg/dl, Females < 50 mg/dl	Lipid profile test
Triglycerides	Serum concentration of triglycerides in milligrams per deciliter (mg/dl)	Quantitative Continuous Ratio	It is considered an alteration when: Males >150 mg/dl Females >150 mg/dl	Lipid profile test

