After forming the (A) control and (B) experimental groups, they will be divided to provide them instructions for compliance with the exercise program while maintaining single-blind conditions. In the control group (A), the exercise prescription used by Habibzadeh in 2010 will be implemented: which involves walking for 30 minutes at an intensity of 57% to 76% of the maximum heart rate, three times per week (Monday, Wednesday, and Friday) for eight weeks (*annex 11*). They will always be accompanied by a previously trained physical education student (Monitoring the intensity range in which the subjects must be during the session, will be done through the effort perception scale (*Annex 12*), heart rate at 15 seconds multiplied by 4 or the H10 polar monitor) (83). On the other hand, the experimental group (B) will engage in an aerobic exercise program (jogging, aquatic activities, and stationary cycling) lasting 40 to 60 minutes, three times per week (Monday, Wednesday, and Friday) for eight weeks, always under the supervision of the principal investigator. Each participant in the experimental group will receive a structured exercise prescription tailored to their specific condition, considering the established aerobic training ranges (57% to 63% of maximum heart rate) (*annexe 11*). (Monitoring the intensity range in which the subjects must be during the session will be done through the effort perception scale (*Annex 12*), heart rate at 15 seconds multiplied by 4 or the H10 polar monitor).

By the end of the first four weeks, the second round of assessments and samples will be done, taking into consideration: Abdominal circumference (*annexe 7*), blood pressure (*annexe 8*), blood collection by venipuncture for HDL, triglycerides and glycemia (*annexe 9*), and the Queen's College step test will be performed (3 minutes) (*annexe 10*), (after completing all the tests, every participant will receive refreshments and will be asked if they are in good

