condition to conclude their assessments, if not, they will be monitored until their answer is affirmative). Subsequently, after completing sample collection and assessments, the control group (A) will continue with the same dynamics as in the initial weeks. The experimental group (B) will maintain the same exercises (jogging, aquatic activities, and stationary cycling), but their intensity may be adjusted from 64% to 76% of the maximum heart rate if favourable results are obtained from the cardiorespiratory fitness test (*annexe 11*), since this shows the level of evolution of the subject after the initial intervention and thus, the FITT-VP principle in exercise prescription would be fulfilled.

At the end of the last 4 weeks of the aerobic physical exercise program, the same sampling will be concluded; Abdominal circumference (*annexe 7*), arterial pressure (*annexe 8*), blood collection by venipuncture for HDL, triglycerides and glycemia (*annexe 9*), and the Queen's College step test will be performed (3 minutes) (*annexe 10*) (after completing all the tests, every participant will receive refreshments and will be asked if they are in good condition to conclude their assessments, if not, they will be monitored until their answer is affirmative), finishing the proposed intervention protocol.

10. Study flowchart

11. Statistical analysis

The statistical analysis will be conducted using the Statistical Package for the Social Sciences (SPSS) Statistics 26 from Business Machine (IBM). Descriptive statistics will be carried out, including measures of central tendency for the variables of age, sex and IPA-Q. Normality tests will be applied such as Kolmogorov-Smirnov for samples > 50 , and Shapiro-Wilk for samples < 50 . For the levels of triglycerides, glucose, HDL (High-Density Lipoprotein), abdominal circumference, and cardiorespiratory fitness, paired-sample T-tests will be used if the data follow a normal distribution, but if they do not, the Wilcoxon signed-rank test will be employed. To compare the control and experimental groups, independent-sample t-tests will be used if the data is normally distributed, otherwise the Mann-Whitney U test will be used. Likewise, a multivariate analysis will be carried out to relate the influence of physical exercise

on metabolic alterations. A significance level of $p \leq 0.05$ will be considered statistically significant.

12. Ethical considerations

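### Hi is met by an effect on any one disorder, but section 11 tests outcomes separately at 0.05 with no primary outcome, multiplicity control or rule for deciding Hi

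*Combined protocol and SAP*

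**What the plan says.** **Section 5.3 (Hypothesis).** Hi is that the eight-week programme "will have effects on at least one of the levels of metabolic disorders", introduced with such as and followed by blood pressure, abdominal obesity, glucose and HDL. H0 is no effect on any of them.

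**Section 11 (Statistical analysis).**
- Within-group paired t or Wilcoxon tests are planned "For the levels of triglycerides, glucose, HDL (High-Density Lipoprotein), abdominal circumference, and cardiorespiratory fitness". This is the only outcome list for the tests, and blood pressure is not on it.
- Between groups: "To compare the control and experimental groups, independent-sample t-tests will be used if the data is normally distributed", otherwise Mann-Whitney. Neither outcomes nor time point are given.
- In addition, "a multivariate analysis will be carried out to relate the influence of physical exercise" on metabolic alterations. No model, outcome set or role is stated.
- A result with p ≤ 0.05 "will be considered statistically significant". Sidedness is not stated.

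**Section 9 (Study Procedure).** Outcomes are measured at baseline, at mid-programme ("By the end of the first four weeks, the second round of assessments and samples will be done") and at the end of week 8.

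**Section 6.2 (Sample size).** Alpha 0.05, power 80%, K = 6.2, means 131.31 and 116.90, SDs 22.53 and 12.88, giving 20 and then 24 per group. Section 2.4 shows that these are pre and post triglyceride values from a cited study.

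No section designates a primary outcome.

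**The concern.** An at-least-one alternative against a joint null is the setting in which unadjusted testing inflates the error of the main claim itself. Each extra outcome gives another chance to support Hi, and the 5% level holds for each test but not for the conclusion.

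Because no rule ties the results to Hi, the outcome, comparison or analysis that carries the trial's only hypothesis could also be settled after the data are known. A positive conclusion would then have no known false-positive rate.

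**Working it through.** **1. The plan's sample size reproduces, and it is one-sided.**
- Variances: 22.53² + 12.88² = 673.50. Squared difference: (131.31 − 116.90)² = 14.41² = 207.65. Ratio: 3.243.
- n = 6.2 × 3.243 = 20.1, so 20; 20 × 1.20 = 24. Both match section 6.2.
- One-sided 0.05 with 80% power gives K = (1.645 + 0.842)² = 6.18. Two-sided 0.05 gives (1.960 + 0.842)² = 7.85, and n = 7.85 × 3.243 = 25.5, so 26 before dropout. The plan's K is the one-sided value.

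**2. Number of outcomes (k).** Four are named in Hi. Counting systolic and diastolic pressure separately gives five. Adding triglycerides, as specific objectives 1 and 4 do, gives six. One week-8 between-group test is counted per outcome.

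**3. Chance of at least one significant result when nothing is affected.** For independent tests this is 1 − (1 − a)^k, where a is the chance that one test counts. For k = 4 and a = 0.05: 1 − 0.95⁴ = 18.5%. For correlated tests, the test statistics are taken as normal with a common correlation. The documents give no correlations, so 0.7 is an assumption.

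| What counts as support for Hi | Correlation | k = 4 | k = 5 | k = 6 |
|---|---|---|---|---|
| Two-sided 0.05, either direction | 0 | 18.5% | 22.6% | 26.5% |
| Two-sided 0.05, either direction | 0.7 | 13.0% | 14.8% | 16.4% |
| Named direction only, 0.025 per test | 0 | 9.6% | 11.9% | 14.1% |
| Named direction only, 0.025 per test | 0.7 | 6.5% | 7.4% | 8.2% |
| Named direction only, one-sided 0.05 (as K implies) | 0 | 18.5% | 22.6% | 26.5% |
| Named direction only, one-sided 0.05 (as K implies) | 0.7 | 12.0% | 13.5% | 14.8% |

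Simulated two-sided t-tests with 24 per group (40,000 trials per setting) agree: 18.5%, 22.8% and 26.6% at correlation 0, and 13.2%, 14.9% and 16.7% at 0.7. Counting week-4 or within-group tests as well would raise these figures.

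**4. Power on the plan's triglyceride inputs.** Common SD = √(673.50/2) = 18.35; standardised difference = 14.41/18.35 = 0.785. This takes a pre-post change as the between-group difference, which is an assumption.

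| t-test | 24 per group | 20 per group |
|---|---|---|
| One-sided 0.05, unadjusted | 85% | 79% |
| Two-sided 0.05, unadjusted | 76% | 68% |
| Two-sided 0.05/6 = 0.0083 (first Holm step) | 49% | 39% |

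In the plan's own formula, two-sided 0.05/6 gives K = (2.638 + 0.842)² = 12.11 and n = 12.11 × 3.243 = 39.3, so 40 per group before dropout, against 20 in the plan.

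**The case against.** **No sentence says that one significant test confirms Hi.** This is true. A reader might infer that the plan adopts that rule, but the documents only leave it as the natural reading. The error rates above are conditional on it. If it is rejected, the plan still has no rule for its hypothesis.

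**The multivariate analysis could be the global test of H0.** It could, and a prespecified global test would control the error. As written, it has no method, outcome set or link to Hi, so it does not fill the gap.

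**The time point is not really open.** A reader might infer a free choice between weeks 4 and 8. The documents lean against this: Hi refers to an eight-week programme, the specific objectives to post-intervention levels, and section 9 uses the mid-programme fitness test to adjust intensity. Week 8 is the sensible reading, though section 11 should say so.

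**The outcome list in Hi is illustrative.** It is introduced by such as, section 2.1.1 counts triglycerides among metabolic disorders, and specific objectives 1 and 4 list them. Their absence from 5.3 is therefore not a contradiction. It does leave the family of tests undefined, hence the range of 4 to 6.

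**High correlation could remove the inflation.** Only in one case. Counting the named direction at 0.025 per test, the rate falls to 5% at a common correlation of about 0.87, 0.91 or 0.92 for 4, 5 or 6 outcomes. At one-sided 0.05 it is still about 9.3% at those values.

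**The study is small.** It nevertheless states a formal Hi and H0, an alpha and 80% power, and nowhere calls itself exploratory.

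**Conclusion.** The concern holds as a missing decision rule with an inflated error rate. If any single significant week-8 between-group result supports Hi, the false-positive chance is 18.5% to 26.5% for 4 to 6 independent outcomes and 13.0% to 16.4% at correlation 0.7, for two-sided tests counted in either direction. Counting only the named direction at 0.025 per test lowers the independent figures to 9.6% to 14.1%. At the one-sided 0.05 behind K = 6.2 they return to 18.5% to 26.5%. The exact rate is not known, because the plan states neither the sidedness nor the outcome list for the between-group tests, and the correlations are assumed.

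A reader might also conclude that triglycerides are already the de facto primary outcome, and that naming them would cost nothing. The documents do not support this. Triglycerides size the trial but are not named in 5.1, 5.2.1 or 5.3, and moving from the one-sided sizing to a two-sided test lowers power from 85% to 76% at 24 per group and from 79% to 68% at 20.

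This must be fixed before results are seen, because it governs the trial's only hypothesis.

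**What to change.** 1. Keep the at-least-one hypothesis and state in section 11 that Hi is supported if any Holm-adjusted p-value is ≤ 0.05 over a fixed list of week-8 between-group comparisons: systolic pressure, diastolic pressure, abdominal circumference, glucose, HDL and triglycerides. One prespecified global multivariate test of group on the same list is an equal option.
2. State that week-4 and within-group tests do not decide Hi, and say what the multivariate analysis is and what it is for.
3. State the sidedness, reconcile it with K = 6.2 in section 6.2, and restate the 80% power for the chosen rule.

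A single primary outcome is an alternative if the authors prefer it. Choosing triglycerides would mean rewording Hi and naming them in 5.1, 5.2.1 and 5.3.

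**Cost.** The edits are wording in sections 5, 6.2 and 11, but power falls.
- At 24 and 20 per group, two-sided power for triglycerides is about 49% and 39% at the first Holm step with six outcomes.
- A global test on six outcomes, if only triglycerides respond, has 43% to 69% at 24 and 35% to 58% at 20 (assumed correlation 0 to 0.5).
- A single two-sided primary test has 76% and 68%.

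All of these may be optimistic, because the control group also exercises ("walking for 30 minutes at an intensity of 57% to 76% of the maximum heart rate" in section 9). At 75% and 50% of the assumed difference, the single unadjusted two-sided test has 52% and 27% power at 24 per group.

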This study is a simple randomized clinical trial, its **objective** is to evaluate the effect of an aerobic physical exercise program on the reduction of triglycerides, blood pressure, abdominal obesity, altered glucose levels, and the increase in HDL in college-level students at the University of Colima, due to the high prevalence of obesity, a sedentary lifestyle, and physical inactivity in Mexican population, all of which contribute to a high risk for the development of metabolic disorders and cardiovascular diseases. **Methods and Materials:** A simple randomized clinical trial will be conducted with a **sample** of 48 voluntary students from the University of Colima, divided into two groups of 24 people. **Instruments:** IPA-Q questionnaire (*Annex 6*), waist circumference (*Annex 7*), blood pressure (*Annex 8*), blood extraction by a venous puncture for HDL, triglycerides, and blood glucose (*Annex 9*), Queen's College Step Test (*Annex 10*). **Procedure:** Once all the information from the tests is collected and processed, inclusion criteria (*table 2*) will be taken into consideration to obtain the total sample. Simple randomization will be carried out through a bag of sealed envelopes that will contain the letter of the group to which the subject belongs. Each participant will draw an envelope, write their name on it and hand it to the supervisor. Afterwards, these envelopes will be opened and participants will be assigned to the groups following the simple blind criteria, according to the letter on the envelope. The Experimental Group will undergo an aerobic physical exercise (APE) program involving jogging, swimming, and static cycling, three times a week with a duration of 60 minutes per exercise session with a progressive intensity, which will start at 57%-63% of the maximum heart rate (HRmax) in the first 4 weeks of the study, and will increase to 64% -76% in the final four weeks, fulfilling the principle of progressive overload. The control group will perform aerobic physical exercise, which will be walking at 57% to 76% of HRmax. **Expected results:** This intervention will lead to favourable changes in the disorders experienced by the intervention population and, at the same time, confirm the effectiveness of the planned aerobic physical exercise in reducing these risks.

Keywords: Exercise, Obesity, HDL, Triglycerides, Hypertension.

1. Introduction

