2.4. Impact of physical exercise on metabolic disorders

Physical activity (PA) encompasses any bodily movement generated by skeletal muscles, requiring energy expenditure and is categorized into intensity levels: light, moderate, and vigorous(1). In 2022, the World Health Organization (WHO) recommends engaging in PA through planned, repetitive, and directed physical exercise. The goal is to improve and maintain physical fitness, involving body and muscle movement to enhance strength, speed, endurance, or flexibility, thereby promoting cardiovascular health(52). Likewise, PA aims to tailor exercise to individual needs, considering diverse physical capacities, since each person may have their advantages and limitations. Not least, PA aims to maintain proper warm-up, central exercise, and cool-down phases for effective and safe practice, ultimately promoting an active and healthy lifestyle(64).

Sequi in 2020 and Primo in 2022 reaffirmed the importance of physical exercise (PE) in individuals with morbidities related to cardiovascular diseases, as it brings considerable health benefits for those with these disorders(63,64). For instance, a study conducted by Chávez and colleagues in 2021 demonstrated that implementing an aerobic physical exercise program (such as walking, jogging, swimming, and dancing) for 20 to 30 minutes over 13 weeks among higher education students in Mexico could significantly reduce parameters associated with metabolic disorders. At the end of his intervention, he led to a considerable reduction of these parameters in this population. The results showed a decrease in abdominal circumference from $110.88\text{cm} \pm 14.27$ in the pretest to $106.90\text{cm} \pm 14.41$ in the posttest, as well

as a reduction in triglycerides from 131.31 mg/dl \pm 22.53 to 116.90 mg/dl \pm 12.88 and a reduction of the alteration in glucose, that went from 94.69 mg/dl \pm 7.98 to 92.50 mg/dl \pm 5.52. The author attributes these results largely to the adequate application of the Frequency, Intensity, Time, Type of activity, and Progression of load (FITT) principles, which are part of exercise prescription(65).

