5.1. Research Question

What is the effect of an aerobic physical exercise program on reducing blood pressure, abdominal obesity, altered glucose levels, and increasing HDL in college-level students at the University of Colima?

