5.2 Objectives

5.2.1 General Objective

To evaluate the effect of implementing an aerobic physical exercise program on the reduction of blood pressure, abdominal obesity, altered glucose levels, and increasing HDL in college-level students at the University of Colima.

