5.2.2. Specific Objectives

1. To establish the prevalence of metabolic disorders (abdominal obesity, triglycerides, HDL, hypertension, and glucose alterations).
2. To determine and compare the post-intervention level of physical activity using the long version of the International Physical Activity Questionnaire (IPAQ).
3. To determine and compare the post-intervention level of cardiorespiratory fitness through the Queen's College Step Test.
4. Compare post-intervention prevalence levels of metabolic disorders (HDL, triglycerides, abdominal fat, hypertension, blood glucose alterations) in higher education students.
5. Determine the level of association between metabolic disorders and cardiorespiratory fitness pre- and post-intervention.

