6.2 Sample size

The sample size was calculated with a formula to compare two means:

$$n = \frac{K(\sigma_1^2 + \sigma_2^2)}{(\mu_1 - \mu_2)^2}$$

Figure 5. Applied formula to calculate the sample size.

Source: Taken from García in 2013(104).

The sample size was determined through a study that assessed the impact of physical training on metabolic alterations. The pre-intervention measurements were 131.31 ± 22.53 , and the post-intervention measurements were 116.90 ± 12.88 (65)

Error $\alpha = .05$

Error $\beta = 0.2$ (20%)

Power $1 - \beta = .8$ (80)

$K = 6.2$

$\sigma^2 = 22.53$

$\sigma^2 = 12.88$

$\mu_1 = 131.31$

$\mu_2 = 116.90$

$n = 20 \pm 20\%$.

$n = 24$ subjects per group

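### The trial is sized on triglycerides, but the research question, general objective and hypotheses do not name them, so the plan leaves open whether a triglyceride result decides the hypothesis

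*Combined protocol and SAP*

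**What the plan says.** Places that leave triglycerides out:

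- 5.1, research question: the effect of the programme "on reducing blood pressure, abdominal obesity, altered glucose levels, and increasing HDL in college-level students".
- 5.2.1, general objective: its effect "on the reduction of blood pressure, abdominal obesity, altered glucose levels, and increasing HDL in college-level students".
- 5.3, Hi: the programme "will have effects on at least one of the levels of metabolic disorders such as: the reduction of blood pressure, abdominal obesity, altered glucose levels", with HDL completing the list. H0 denies an effect on any member of the same list: "the reduction of blood pressure, abdominal obesity, altered glucose levels, and increasing HDL in the study population".

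Places that include them:

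- Abstract: the objective is to evaluate the programme's effect "on the reduction of triglycerides, blood pressure, abdominal obesity, altered glucose levels, and the increase in HDL". The Spanish summary uses the same order.
- 5.2.2: specific objective 1 covers the prevalence of all five disorders. Specific objective 4 reads "Compare post-intervention prevalence levels of metabolic disorders (HDL, triglycerides, abdominal fat, hypertension, blood glucose alterations) in higher education students".
- Section 7, Table 5: triglycerides are a dependent variable with a cut-off.
- Section 9: triglycerides are measured at baseline, after four weeks and at the end.
- Section 11: triglycerides come first among the variables to be tested.

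Section 6.2 does not name its variable. It says only "The pre-intervention measurements were 131.31" (SD 22.53) and gives 116.90 (SD 12.88) afterwards, citing reference 65. Section 2.4 reports from the same reference "a reduction in triglycerides from 131.31 mg/dl", with the same second mean and the same two SDs. Section 3 (Justification) repeats both means as triglycerides in mg/dl.

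No section names a primary outcome.

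**The concern.** A trial's sample size, hypothesis and main analysis should concern the same outcome. Here the only outcome with a sizing calculation is missing from the three statements that say what the trial asks and what it will claim. The four outcomes that are listed have no sizing assumption.

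With no primary outcome, 5.3 is the only text that defines success, and it does so with an 'at least one' claim. Such a claim needs a fixed list of the outcomes that can satisfy it. This list is introduced as examples in 5.3 and given without that qualifier in 5.1 and 5.2.1.

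Suppose triglycerides improve and nothing else does. The authors could report that Hi is supported, because triglycerides are a metabolic disorder, or that H0 stands, because they are not listed. The plan does not choose between these, so the choice could be made after the data are seen.

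**Working it through.** **1. What 6.2 is sized on.** The inputs in 6.2 are means 131.31 and 116.90, SDs 22.53 and 12.88, and K = 6.2. All four means and SDs match the triglyceride figures in section 2.4.

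**2. The plan's own figure.** The formula in 6.2 is n = K(SD1² + SD2²)/(mean1 − mean2)².

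- SD1² + SD2² = 22.53² + 12.88² = 507.60 + 165.89 = 673.50
- Difference = 131.31 − 116.90 = 14.41, and 14.41² = 207.65
- n = 6.2 × 673.50 / 207.65 = 20.11
- 20.11 × 1.2 = 24.1

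The stated 20, and 24 after adding 20%, are reproduced. The 24 per group comes from triglycerides.

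**3. Outcome lists side by side.**

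| Place | Triglycerides named? | How the list is introduced |
|---|---|---|
| Abstract objective | Yes, first | Without 'such as' |
| 5.1 Research question | No | Without 'such as' |
| 5.2.1 General objective | No | Without 'such as' |
| 5.3 Hi and H0 | No | With 'such as' |
| 5.2.2 Specific objectives 1 and 4 | Yes | As prevalence |
| 6.2 Sample size | Used, but not labelled | Not applicable |
| Table 5 | Yes | Dependent variable |
| Section 11 | Yes, first | Tested variable |

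Table 4 also mentions elevated triglycerides, but as an eligibility condition, so it does not bear on which outcomes are tested.

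**4. Does the sizing carry over to the listed outcomes?** Section 2.4 gives means and SDs from the same cited study for two of the four. The same formula with K = 6.2, before any inflation, gives:

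- Abdominal circumference, 110.88 ± 14.27 to 106.90 ± 14.41: 6.2 × (14.27² + 14.41²)/3.98² = 6.2 × 411.28/15.84 = about 161 per group.
- Glucose, 94.69 ± 7.98 to 92.50 ± 5.52: 6.2 × (7.98² + 5.52²)/2.19² = 6.2 × 94.15/4.80 = about 122 per group.

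At 24 per group on these figures, power is about 25% one-sided (16% two-sided) for circumference and about 30% (20%) for glucose. For triglycerides it is 86% (78%). K = 6.2 corresponds to a one-sided 0.05 test with 80% power, since (1.645 + 0.842)² = 6.18. All of these figures treat one group's before-and-after values as a between-group difference, as 6.2 does, so they are illustrative. The plan gives no comparable figures from that study for HDL or blood pressure.

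**5. Effect of adding a fifth outcome without choosing a primary.** Assume one test per outcome at 0.05, independence and no adjustment. The chance of at least one false positive is 1 − 0.95⁴ = 18.5% with four outcomes and 1 − 0.95⁵ = 22.6% with five.

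**The case against.** The strongest reply is that H0 already covers triglycerides. It denies an effect on any metabolic disorder, with the four outcomes given as examples. Section 2.1.1 and Table 1 class raised triglycerides as a metabolic disorder, and so do specific objectives 1 and 4. The Justification uses the same loose 'such as' for the class, in a list that includes triglycerides and omits HDL. On that ordinary reading a triglyceride effect contradicts H0.

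This reply stands far enough to rule out a stronger reading. A reader might infer that, as written, a clear triglyceride effect would leave H0 standing. The documents do not support that, because the wording of 5.3 leaves triglycerides' status open and does not exclude them. The reply does not settle the matter either. The same four-item list appears in 5.1 and 5.2.1 without the qualifier, and an open-ended list is itself unsuitable for an 'at least one' hypothesis.

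A reader might also infer that triglycerides have dropped out of the plan. They have not. They are measured at every assessment and tested in section 11, so the freedom after the fact concerns only whether they count toward the hypothesis. The specific objectives do not supply that answer, because they concern prevalence and 6.2 is built on a difference in means.

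It can also be said that naming triglycerides gives the other four outcomes no sizing, and that a fifth outcome adds to multiplicity. Both are true, and they are the reason the change should include the choice of a primary outcome.

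**Conclusion.** The concern holds as an inconsistency that leaves the decisive outcome undefined. The sizing outcome is one of five metabolic outcomes. It is named first in the abstract and in none of the research question, general objective, Hi or H0. None of the four outcomes listed there has a sizing assumption. For the two that can be checked from the cited study, 24 per group falls well short of the roughly 161 and 122 that the plan's own formula would require, subject to the before-and-after caveat above.

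That 6.2 uses triglycerides rests on an exact match of two means and two SDs to values labelled as triglycerides in section 2.4, from the same reference. The conclusion that their status is open rests on the differing wording of 5.1, 5.2.1 and 5.3 and on the absence of a named primary outcome. It does not depend on the illustrative power figures.

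Nothing suggests that the omission was deliberate. It still matters, because these sentences define the confirmatory claim and correcting them loses its value once results are known.

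**What to change.** Before any follow-up data are seen, which means before the week-4 results:

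1. Add triglycerides to 5.1, 5.2.1, Hi and H0.
2. In Hi and H0, replace 'such as' with a closed list of the five outcomes.
3. In 6.2, label the variable as triglycerides (mg/dL).
4. State that triglycerides, the outcome the trial is sized on, are the primary outcome and that the other four are secondary. Word the 'at least one' clause to agree, so that the confirmatory conclusion rests on triglycerides.

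The cost is a few sentences. There are no new data, visits or participants, and this change leaves 24 per group as it is. The one downside arises if step 4 is omitted. Five outcomes would then sit under 'at least one' at p ≤ 0.05 without adjustment, and the false-positive chance would rise from about 19% to about 23% on the assumptions shown. Naming a single primary outcome avoids this.
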